- Interval history and adverse event review
- Physical exam
- Blood collection as outlined in table 1
- Urine pregnancy testing

Visit 3

Visit 3 will take place 16 weeks after a subject starts taking study medication and will require about one hour. The following testing will be obtained at this visit:

- Interval history and adverse event review
- Physical exam
- Blood collection as outlined in table 1
- Urine pregnancy testing

Visit 4

Visit 4 will take place at 24 weeks after the start of therapy and after this visit the subject will stop taking the medication. This visit will require about 5 hours. The following testing will be obtained at this visit:

- Medical history
- Full physical examination
- Medication reconciliation
- Blood collection as outlined in table 1
- Urine pregnancy testing
- MRI of the abdomen if angiomyolipoma or any other kidney abnormalities are present on screening MRI
- St. George's Respiratory Questionnaire (SGRQ)
- Spirometry, Post Bronchodilator spirometry, body plethysmography and diffusing capacity for carbon monoxide (DLCO)
- Collection of exhaled breath condensates

Early termination study visit

If a subject decides to stop taking part in the study for any reason, she will make a final study visit. The final study visit will take about 6 hours. The following testing will be obtained at this visit:

- Medical history
- Full physical examination
- Medication reconciliation
- Blood collection as outlined in table 1
- Urine pregnancy testing
- MRI of the abdomen if angiomyolipoma are present on screening MRI
- St. George's Respiratory Questionnaire (SGRQ)
- Spirometry, Post Bronchodilator spirometry, body plethysmography and diffusing capacity for carbon monoxide (DLCO)
- Collect any unused study drug and drug diaries
- Collection of exhaled breath condensate

Subject study participation may be discontinued by the PI if:

- At the PI's discretion in the best interest of the subject
- Subject can't make study visits
- The sponsor decides to stop the study
- The subject has intolerable side effects even at the lower dose of Celecoxib
- Subject becomes pregnant
- Subject does not follow study requirements

Labs performing evaluations and special precautions

The clinical laboratory evaluations will be performed in CLIA approved laboratories at BWH and the NIH Clinical Center.

Investigational analyses of VEGF-D and circulating LAM cells will be conducted in research laboratories at BWH and NIH.

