- i- VEGF-D analysis will be performed in [name] laboratory at BWH
- ii- Next generation sequencing (NGS) assay to detect TSC2 mutant LAM cells in FACS sorted circulating LAM cells and/or TSC2 mutations in plasma cell-free DNA will be performed at BWH in [name] laboratory

Transfer of specimens between sites will be necessary to complete the investigational analyses. Samples will be shipped overnight on dry ice Monday to Thursday to keep specimens frozen. Transferring site will keep a log of all specimens transferred. The receiving site will keep a log of when samples are received and analyzed.

Primary outcome measurements

We will perform a two-center phase I trial of celecoxib (COX-2 inhibitor) administered at 200mg by mouth daily for 6 months. A study investigator will obtain informed consent after detailed review of the consent form with potential study participants. Consenting subjects will be screened at the initial visit based on predefined inclusion/exclusion criteria. Subjects must have mild to moderate LAM (defined as definite LAM not requiring rapalog therapy), have no history of chronic non-steroidal anti-inflammatory drug use, have no previous history of treatment with rapamycin or everolimus, and have no angiomyolipoma of diameter > 4 cm. Enrolled subjects will receive celecoxib at an initial dose of 200 mg orally daily, with a single dose adjustment to 100mg PO QD permitted if needed.

Any subject who receives at least one dose of celecoxib will be included in the analysis for side effects. Dose limiting toxicity will be graded according to the National Cancer Institute's CTCAE v3.0 (http://ctep.cancer.gov/protocoldevelopment/electronic_applications/docs/ctcaev3.pdf). During the 6 months of the trial, there will be 3 study related visits. Clinical and laboratory evaluation is described below.

Since this dose of celecoxib (200mg PO QD) is routinely well tolerated in the clinical setting in patients with arthritis and other inflammatory disorders, we expect that it will be well-tolerated in LAM patients. However, we will carefully monitor GI tolerance and renal function, since celecoxib can lead to reversible renal impairment.

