Care. The investigators will be responsible for alerting the sponsor to any event that seems unusual, even if the event may be considered an unanticipated benefit to the subject. By exercising appropriate health-care options, the investigator remains responsible for managing AEs that are serious or that cause the subject to discontinue before completing the study. Frequency of follow-up beyond that mandated in the protocol is left to the discretion of the investigator.

Confidentiality and HIPAA considerations

All subjects must provide written informed consent and signed HIPAA authorization prior to the performance of any screening or main study procedures. Subject confidentiality will be protected throughout the study and no subject-identifying information will be released to anyone outside the project. Confidentiality will be secured through several mechanisms. Each subject will be assigned an anonymous study ID, which will be used on all study forms. Any study forms and paper records containing personal identifier information (e.g., address, phone number) will be kept secured and locked at each clinical site. No personal identifiers will be placed on biological samples and other documents forwarded to central labs and reading centers.

Access to all subject data and information at the clinical sites, including biological samples, will be restricted to authorized personnel. Only authorized personnel at the coordinating center will have access to study data files. Authorized personnel will be assigned user logon IDs, passwords and appropriate access privileges to study data. Study subjects will be identified only by their initials and subject ID number. No personal identifiers such as name, address, social security number will be entered into the study database. Any subject-specific data reported to any study committees will only be identified by subject ID number.

Finally, subjects will not be identified by name in any reports or publications, nor will the data be presented in such a way that the identity of individual subjects can be inferred. Analysis files created for further study by the scientific community will have no subject identifiers.

Protection against subject risks related to the study medication

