- Is life threatening (places the subject at immediate risk of death from the event as it occurred)
- Requires inpatient hospitalization or prolongation of existing hospitalization
- Results in a persistent or significant disability/incapacity
- Results in a congenital anomaly/birth defect or
- Any other adverse event that, based upon appropriate medical judgment, may jeopardize the subject's health and may require medical or surgical intervention to prevent one of the outcomes listed above.

Important medical events that may not result in death, be life-threatening, or require inpatient hospitalization may be considered an SAE when, based on appropriate medical judgment, they may jeopardize the subject and may require medical or surgical intervention to prevent one of the outcomes listed above.

An Unexpected Adverse Event is an adverse reaction, the nature or severity of which is not consistent with the applicable product information per the Investigator Brochure.

Life-threatening means that the subject was, in the view of the investigator, at immediate risk of death from the AE as it occurred. It does not include an AE that, had it occurred in a more severe form might have caused death.

Persistent or significant disability/incapacity means that the event resulted in permanent or significant and substantial disruption of the subject's ability to carry out normal life functions.

Associated with the use of the drug means there is reasonable possibility that the AE may have been caused by the drug.

Adverse event reporting

All AEs (serious and non-serious) will be recorded from start of study treatment (enrollment) through final study visit on the AE case report form.

All adverse events will be reported to the Partners Human Research Committee (PHRC) in accordance with the accepted guidelines. A 24-hour/7-day telephone number will be provided for contacting the licensed physician investigator for this purpose.

The research staff will monitor all subjects during their study involvement for evidence of any adverse events. Local study site personnel will report all serious adverse events (SAEs) to a designated medical monitor who will collect initial reports and oversee medical record retrieval for determination of final diagnosis.

Serious Adverse Events Reporting

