All deaths and all SAEs require reporting from the start of treatment through 28 days after discontinuation of the study. The site is required to call the coordinating center to inform them of the SAE within the 24 hours of knowledge of the event. The site should also submit an SAE form via fax to the coordinating center and enter the SAE information onto the CRF within 24 hours of knowledge of the event.

An updated full written report will be filed as additional information becomes available within 10 working days (14 calendar days). The report will include a complete description of the event, use of all concomitant medications, and the local investigator's assessment of causality of the SAE. Non-serious adverse events will be reported at routine visits, documented on a separate adverse event form, and transmitted to the central coordinating center. All serious and unexpected adverse events will be reported to the overall study PI's.

Expedited Event Reporting

Adverse events that meet the definition of serious, study drug-related and unexpected (per the Investigator's Drug Brochure) qualify for expedited reporting to the regulatory authorities. The DSMB will perform a medical review of all deaths and study drug-related serious adverse events and evaluate for "unexpectedness".

The coordinating center will prepare Med Watch reports for those events identified as serious, study drug-related and unexpected as determined by the DSMB. The coordinating center will submit all unexpected study drug related SAEs as per 21 CFR 32.

Safety events requiring expedite reporting will be sent to the DSMB chair, with forwarding by the chair to the full board as needed, and DOD program office within 1-2 business days. DSMB chair will respond to the overall principal investigator and the coordinating center within 48 hours. Reporting framework and timelines are to be documented in Data and Safety Monitoring Plan after consultation with board members.

Coding for Adverse Events

All reported adverse events will be classified using the Common Terminology Criteria for Adverse Events (CTCAE), version 4.

X- References

Anonymous. (1991). "Lung function testing: selection of reference values and interpretative strategies. American Thoracic Society." Am Rev Respir Dis **144**(5): 1202-1218.

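### For women who complete treatment, no recording of non-serious adverse events and no chemistry is planned after celecoxib stops, so off-drug resolution is not systematically captured

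*Combined protocol and SAP*

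**What the plan says.** The relevant statements lie in several sections of the combined protocol and SAP.

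- **Recording window** (Adverse event reporting, in part d of Monitoring and Quality Assurance): "All AEs (serious and non-serious) will be recorded from start of study treatment (enrollment) through final study visit on the AE case report form".
- **Last visit** (Visit 4 entry in section V): "Visit 4 will take place at 24 weeks after the start of therapy and after this visit the subject will stop taking the medication".
- **Chemistry** (section V, Table 1): liver and renal tests at baseline and weeks 8, 16 and 24. There is no later column.
- **Non-serious events** (Serious Adverse Events Reporting): "Non-serious adverse events will be reported at routine visits".
- **Serious events** (same section): "All deaths and all SAEs require reporting from the start of treatment through 28 days after discontinuation of the study". An updated written report follows, with the local investigator's view of causality.
- **Renal effect** (section V, Primary outcome measurements): renal function is singled out for monitoring, "since celecoxib can lead to reversible renal impairment".
- **Anything further** (section VII, Protection against general subject risks): "Frequency of follow-up beyond that mandated in the protocol is left to the discretion of the investigator".

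**The concern.** Section II makes safety and tolerability the main objective, and the trial has no control arm. What happens to an event once the drug is withdrawn is then among the more useful pieces of evidence on whether the drug caused it. Every completer stops celecoxib at a known time, so the information is close at hand. Yet the recording rule, followed exactly, closes the form while she is still on drug.

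The protocol's definitions count an abnormal laboratory finding as an adverse event. A raised creatinine in the week-24 blood is therefore a recordable event with no planned later value and no planned outcome. Section VII adds that the package insert gives no rate for renal toxicity, so the trial's own renal data carry some weight. A final report might list such events without being able to say whether they reversed, which would serve poorly the later phase II/III studies that this pilot is meant to enable.

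**Working it through.** **1. The plan's own figure.** Table 2 gives the chance of at least one event in 12 subjects. The formula is 1 − (1 − p)^12.

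| Rate p | Calculation | Result | Table 2 |
|---|---|---|---|
| 6% | 1 − 0.94^12 | 52.4% | 52% |
| 2.5% | 1 − 0.975^12 | 26.2% | 26% |
| 0.2% | 1 − 0.998^12 | 2.37% | 2.3% |

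The table reproduces, apart from the rounding of the last entry. This point disputes none of these figures.

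**2. The windows side by side, for a completer.**

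| Item | Last planned collection | Planned time off drug |
|---|---|---|
| Non-serious events | Week-24 visit, on drug | 0 days |
| Kidney and liver tests | Week-24 visit, on drug | 0 days |
| Deaths and serious events | 28 days after study discontinuation | 28 days, if counted from the last dose or from Visit 4 |

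The phone calls in Study Procedures fall between visits, so none is planned after Visit 4. A change found at week 8 or 16 is measured again, but on drug unless dosing was interrupted or stopped. A change first found at week 24 is not measured again under the schedule.

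**3. Two rules that do not agree.** The first rule closes the form for serious and non-serious events alike at the final visit. The second carries serious events to 28 days after study discontinuation, and does not say whether that means last dose or last visit. For an early leaver the two dates could differ, because the interval from last dose to the early termination visit is not stated.

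**4. Illustrative size.** The documents give no onset times. Assume a constant onset hazard over the 24 weeks, and treat the Table 2 rates as applying to that period. The share first seen at the last draw is (24 − 16)/24 = 8/24 = 1/3. The chance that at least one of 12 women has an event of a given type first found at week 24 is 1 − (1 − p/3)^12:

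- p = 6%: 1 − 0.98^12 = 21.5%
- p = 2.5%: 1 − 0.99167^12 = 9.6%
- p = 0.2%: 1 − 0.99933^12 = 0.8%

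The 6% and 0.2% rates are those that section VII gives for borderline and significant liver enzyme elevation, so those two lines apply directly to a laboratory change. If the share is not 1/3 it can lie anywhere from 0 to 1, and the 6% line then lies between 0% and 52.4%. Events that began earlier and are still open at week 24 would add to these figures. The documents give no durations from which to count them.

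**The case against.** The strongest reply is that much of the evidence is already there.

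- Each woman has a baseline and three on-drug chemistry values.
- A drug-related event allows one dose reduction, with withdrawal if symptoms persist, which amounts to a partial dechallenge. Section VII also refers to dose interruption.
- Serious events have the 28-day window, record retrieval and this provision: "An updated full written report will be filed as additional information becomes available within 10 working days (14 calendar days".
- Early leavers have a final visit with bloods, which may fall after the last dose.
- Investigators may follow anyone further.
- The stated safety variable is incidence, which needs no resolution date.
- The stopping and expedited-reporting rules concern mainly serious events. The exception is a grade IV toxicity that is not also serious.

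Most of this stands, and it rules out stronger readings. A reader might infer that off-drug resolution is never recorded, or that it is the only within-subject evidence on causality. The items above contradict both. A reader might also infer that every non-serious event open at the last dose will be reported with an unknown outcome. The documents do not show the fields of the adverse event form, and the data management section requires sites to correct or update the database to resolve discrepancies. An update to an existing entry is not barred.

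The reply does not close the gap for completers. The 28-day window covers deaths and serious events only. Dose reduction keeps the woman on drug and cannot help with a change first seen at week 24. Discretionary follow-up at two sites creates no duty to record, so it cannot be summarised reliably.

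**Conclusion.** The point holds for completers, and for non-serious events and kidney or liver changes present at week 24. Whether these resolve off drug is not systematically captured. It rests on the recording rule, the timing of Visit 4 and Table 1 read together, and on no numerical assumption.

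The numerical size is illustrative only. One third of new laboratory changes would first be seen at week 24 if the onset hazard is constant. That corresponds to a chance between 0.8% and 21.5%, over the Table 2 rates, that any of 12 women is affected by a given event type. For any one type, the likeliest number affected is zero. This is a cheap improvement to a small pilot, not a flaw that undermines its incidence results. The mismatch between the two recording windows is a separate matter of wording and needs reconciling in any case.

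**What to change.** 1. Amend the adverse event reporting section so that events ongoing or first found at the final visit stay open on the form until resolved or until 28 days after the last dose. Obtain outcome and date by phone and record review.
2. Record any creatinine or liver value obtained off drug in that window. This mandates no new test, so reversal of a laboratory change will be known only where a value exists. Report how many women had none.
3. Report the numbers resolved and ongoing off drug beside the incidence.
4. Reconcile the rule that ends all recording at the final visit with the 28-day rule for serious events, and define that rule's starting point as last dose or last visit.

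The cost is a wording change, an outcome and date field if the form lacks one, and one brief contact for each woman with an open event. The sample size and Table 2 are unchanged.

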The subject will be given the opportunity to take the consent home to consider participation. The subject will be asked to read the informed consent form prior to the physician or study coordinator asking the subject any questions concerning their health. Written, informed consent will be obtained after one of the investigators has reviewed the protocol verbally in detail with the subject. The physician will inform the subject that she has the alternative not to participate in the study. Subjects will receive a signed copy of the consent form for their records. After all questions are answered, and only after the consent form is signed by the patient and one of the MDs listed on the application will study screening commence. Subjects unable to give consent will not be approached.

Participation in other trials

Subjects will be allowed to participate in other research studies, as long as they do not involve the use of an investigational therapy.

Inclusion of Women and Minorities in this study

Adult women (>18 years of age) without any restrictions on age, race or ethnic group are eligible to participate in this trial. We will make every attempt to reach women of all ethnic groups, by advertising broadly through patient groups, LAM foundation and the internet.

V- Study procedures

Prior to enrolling in the study subjects must undergo the following tests to determine eligibility and baseline characteristics.

Screening and baseline testing		Timing prior to start of therapy
Informed consent	To be obtained before entry	
Medical history and physical examination	Including weight, height, SaO ₂ , vital signs (heart rate, blood pressure, temperature)	Within 28 days
Hematology	Complete blood count and differential (CBCD)	Within 28 days
Serum chemistries	Must include alkaline phosphatase, AST, ALT, bilirubin, serum creatinine, calcium and magnesium	Within 28 days
Urine test	Including pregnancy test	Within 28 days
Electrocardiogram (ECG)		Within 28 days
Pulmonary function test	Spirometry, Post Bronchodilator spirometry, TLC, DLCO	Within 28 days
Abdominal MRI		Within 3 months

Study Visit Summary

Study Procedures

All study procedures will be performed in accordance with accepted standards of practice. Relevant changes in clinical status and medication use, symptom history and adverse events will be reviewed at each study visit and in between study visit by a phone call placed from the research team to subjects enrolled in the study.

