Blood samples (chemistry, CBC) and biomarkers (VEGF-D, circulating TSC2 mutant cells) will be obtained via blood draws at indicated study visits. In addition, urine pregnancy testing will be performed at each study visit during the course of drug administration. Pulmonary function testing will be performed in accordance with ATS guidelines (Anonymous 1991) and according the schedule outlined in Table 1. Abdominal MRI will be performed at enrollment –if not done in the past 3 months-, and if angiomyolipoma or any other kidney abnormalities are detected, follow-up MRI will be performed at the discretion of the study team as indicated in Table 1. The St. Georges Respiratory Questionnaire (SGRQ) will also be administered and scored in accordance with published guidelines (Barr et al. 2000). Information on hospitalization and side effects will be obtained via direct subject interviews and medical record review.

Table 1: study visits and testing

Week

	Baseline	8	16	24
Visit number	1	2	3	4/early termination
Informed consent	X			
History and physical	X	X	X	X
Concurrent Medication Reconciliation	X	X	X	X
Adverse Event Review	X	X	X	X
Drug Administration Record	X	X	X	X
Liver, renal, glucose, cholesterol	X	X	X	X
EKG	X			
Urine pregnancy	X	X	X	X
CBC diff	X	X	X	X
MRI abdomen	X			X
Full PFT	X			X
St George's questionnaire	X			X
Stored serum and plasma	X	X	X	X
Exhaled breath condensate	X			X
measurement of TSC2 mutant cells	X			X

Study Windows

The screening to first dose period will be 28 days. All other study visit windows will be +/- one week.

Study visit procedures

Screening Visit (Visit 1)

The Screening Visit will take about 5 hours.

The following testing will be performed at the screening visit:

- Medical history
- Full physical exam
- Medication reconciliation
- Blood collection as outlined in table 1
- Urine pregnancy testing
- EKG
- MRI of the abdomen if not done in the last 3 months
- St. George's Respiratory Questionnaire (SGRQ)
- Spirometry, Post Bronchodilator spirometry, body plethysmography and diffusing capacity for carbon monoxide (DLCO)
- Stored blood for all exploratory endpoints
- Collection of exhaled breath condensates

Subjects who meet the inclusion criteria will be enrolled in the study and will start taking their medications

Visit 2

Visit 2 will take place 8 weeks after a subject starts taking study medication and will require about one hour.

The following testing will be obtained at this visit:

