We will perform assessments of clinical, functional and subject self-reported outcomes to assess potential benefit of celecoxib. Since lung function decline is a hallmark of LAM, we will perform spirometry, which will be interpreted in accordance with standard guidelines (Anonymous 1991). We will utilize the St. George's Respiratory Questionnaire (SGRQ) (Barr et al. 2000), as an assessment of the impact of treatment on dyspnea levels. Finally, we will record the incidence of hospitalization, complications from the disease, and other medical problems occurring during the study period

Stopping rules

The study will be monitored for the occurrence of a specified set of treatment related serious adverse events (TRSAE). The following two types of TRSAEs will be considered for early stopping of the study:

- Death considered to be probably or definitely related to Celecoxib

- Any grade IV toxicity considered to be probably or definitely related to Celecoxib

Subjects will be followed for 24 weeks while on therapy. During the 24 weeks of the trial, there will 4 study visits (screening visit and 3 visits while on therapy). Clinical and laboratory evaluations will be performed as outlined in Table 1.

Secondary outcome measurements

We will be performing several correlative studies as part of this protocol.

- a. VEGF-D levels. VEGF-D is well-known as a biomarker of LAM, and disease extent correlates with VEGF-D levels. Therefore we will measure VEGF-D prior to treatment and at serial time points during treatment. As this is a pilot study, formal statistical analysis is not planned.
- b. Circulating LAM cells. Circulating LAM cells may be isolated from peripheral blood of subjects on this trial, using density gradient and FACS methods. TSC2 mutations will be identified in these cells, if possible, and then the prevalence of LAM cells will be measured serially over time in subjects on this study. If no TSC2 mutation is identified, then mutations in other genes in this pathway (RHEB, MTOR) will be sought. However, we will not scan the entire genome in these analyses, but rather focus on just a few genes. We will test the number of circulating LAM cells over time to help assess whether the treatment, celecoxib, reduces the number of LAM cells.

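### Deaths and SAEs are reportable for 28 days after discontinuation, but the AE form and all scheduled contact stop at the final visit

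*Combined protocol and SAP*

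**What the plan says.** Two parts of section IX d (Monitoring and Quality Assurance) set different end dates for serious events. Under Serious Adverse Events Reporting: "All deaths and all SAEs require reporting from the start of treatment through 28 days after discontinuation of the study". The part headed Adverse event reporting stops sooner: "All AEs (serious and non-serious) will be recorded from start of study treatment (enrollment) through final study visit on the AE case report form".

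The contact schedule in section V follows the earlier date. The last column of Table 1 is "4/early termination" at week 24. The visit description reads "Visit 4 will take place at 24 weeks after the start of therapy and after this visit the subject will stop taking the medication". The text after the stopping rules says "Subjects will be followed for 24 weeks while on therapy" and counts one screening visit and three on-therapy visits, with none off drug. Under Study Procedures, changes in clinical status, medication, symptoms and adverse events "will be reviewed at each study visit and in between study visit by a phone call placed from the research team".

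A woman who chooses to leave makes one final visit. Its timing relative to her last dose is not given, and no later contact is listed.

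**The concern.** Aim 1 puts safety and tolerability first, and every woman who takes at least one dose enters the side-effect analysis. The plan creates a 28-day duty to report deaths and SAEs but schedules no step that would bring such events to the site's notice. The 24-hour reporting clock runs from when the site learns of an event, so it does not fill the gap.

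Women whose symptoms persist at the reduced dose are withdrawn. Those with unresolved toxicity may therefore be the ones who pass earliest into the period without scheduled contact. The early termination visit is described for a subject who decides to stop, so its application to women withdrawn by the PI is not explicit.

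At stake is how a zero would be read. If no SAE is recorded after the last visit, a reader could not tell whether none occurred or none was sought. It is also unclear which form a late SAE belongs on, because the AE form has closed by then.

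**Working it through.** The plan gives no figure for this point. Its only sample-size figures, in Table 2, do not enter the argument. They reproduce to within rounding: 1 − (1 − p)^12 gives 52.4%, 26.2% and 2.37% for p = 6%, 2.5% and 0.2%, against 52%, 26% and 2.3% stated.

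**Inputs.** Treatment of 24 weeks, with the drug stopping after Visit 4 (section V, Visit 4); visit window of ± 1 week (Study Windows); SAE period of 28 days after discontinuation (Serious Adverse Events Reporting); 12 subjects (Sample Size Considerations).

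**Which contacts fall after the last visit?**
- Table 1: none; it ends at Visit 4 or early termination.
- Staff telephone calls: none; they are placed between visits.
- AE form: closed at the final visit.
- Subject-initiated calls: possible, but passive.
- Investigator follow-up beyond the protocol: discretionary.
- Medical record review for hospitalization and side effects: no timing stated.

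**Completer, under the 28-day rule.**
- Scheduled follow-up: 24 × 7 = 168 days.
- SAE window: 168 + 28 = 196 days.
- Share with no scheduled contact: 28/196 = 14.3%.
- With Visit 4 one week early: 28/(161 + 28) = 28/189 = 14.8%.
- With Visit 4 one week late: 28/(175 + 28) = 28/203 = 13.8%.
- Over 12 completers: 12 × 28 = 336 subject-days, or 336/365.25 = 0.92 subject-years.

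**Completer, under the AE-form rule.** The window closes at the final visit, so the uncovered time is 0 days.

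**Early leaver.** Let T be the day of last dose and d the days from last dose to the final visit; d is not stated.
- Anchor at last dose: uncovered days = max(0, 28 − d), window = T + 28.
- Anchor at leaving the study, taken as the final visit: uncovered days = 28, window = T + d + 28.

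As an illustration, take T = 56 (week 8):

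| d (assumed) | Anchor at last dose | Anchor at leaving study |
|---|---|---|
| 0 | 28/84 = 33.3% | 28/84 = 33.3% |
| 14 | 14/84 = 16.7% | 28/98 = 28.6% |
| 28 | 0/84 = 0% | 28/112 = 25.0% |

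**Rough scale of drug-related risk in the gap.** The rates come from section VII a. I assume a constant hazard, the on-drug rate continuing off drug, and no detection by any other route.
- Cardiovascular, 2.5% over 3 years: 0.025 × 336/1095 = 0.008 events.
- Complicated and symptomatic ulcers, 0.78% at 9 months (about 274 days): 0.0078 × 336/274 = 0.010 events.
- Together: about 0.02 expected events in 12 women.

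This leaves out LAM-related SAEs, and the protocol says that celecoxib side-effect rates in LAM are unknown.

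**The case against.** The strongest reply is that the gap exists only under one of the two stated end dates. If the sponsor meant serious events to be collected through the final visit, nothing is uncovered. That stands, and it is why the two sections must be reconciled first. A reader might infer that the flaw persists whatever end date is chosen; the AE-form sentence rules that out.

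A reader might also infer that late events are counted only if the woman telephones. The documents do not support so absolute a statement. Record review is named as a source of hospitalization data. The investigator remains responsible for managing serious AEs and those that lead to early discontinuation, and may follow up further. Some subjects come from the investigators' own practices, and a 24-hour telephone number is provided. These routes are real, but none is scheduled or required in the 28 days, so they do not make silence informative.

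The Data and Safety Monitoring Plan is to set out the reporting framework and timelines, and it could contain a post-treatment contact. It is not among the documents. If it does contain one, Table 1 should still show it.

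Finally, 14% is a share of calendar time, not of risk, and the rough figure of 0.02 expected drug-related events is small. That limits the weight of the point. It does not remove the mismatch, because the duty covers all deaths and SAEs, related or not.

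**Conclusion.** The point holds as a mismatch between a reporting duty and the contact schedule. Under the 28-day rule, about 14% of a completer's SAE window (13.8% to 14.8% with the visit window) has no scheduled ascertainment. This rests on the 28-day rule being the intended one, on leaving the study nearly coinciding with last dose for completers, and on no contact being specified in the unavailable monitoring plan.

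Two larger figures are tempting and should not be used as the size of the problem. A share of 33% for a woman who leaves at week 8 requires a final visit on the day of last dose, which the protocol does not state; a later visit lowers it, to zero in one case. One missed SAE in 12 women is 1/12 = 8.3 percentage points, but that is true of any missed event at any time and says nothing about this gap.

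This is a worthwhile low-cost improvement to the safety data, not a threat to the trial's validity.

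**What to change.** 1. Reconcile Adverse event reporting with Serious Adverse Events Reporting, so that there is one SAE collection window with a stated anchor: last dose or leaving the study.
2. Extend the AE form to the end of that window, so that late SAEs and outcomes of open events have a place to be recorded.
3. If the 28-day period stands, add to Table 1 and to the Visit 4 and early termination descriptions one documented telephone call at the end of the window. It should apply to every treated woman, including those withdrawn by the PI. Ask about SAEs, hospitalisation, pregnancy and unresolved AEs, and confirm vital status if she cannot be reached.
4. State that the early termination visit applies to PI-initiated withdrawal, and record its date relative to last dose.

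If the call is anchored at last dose, it would fall before either stated end of contraception (30 days after last dose in the inclusion criteria, at least 8 weeks in the risk section). Its pregnancy question would then not cover either period in full. Those two passages differ and also need to be reconciled.

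The cost is protocol wording, a small form change and at most 12 short calls by existing staff, using a type of call that the protocol already describes.
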